#### 9.2.4.2 Laboratory parameters

Not applicable, it is not planned to assess laboratory parameters.

#### 9.2.4.3 Vital signs

Not applicable, it is not planned to assess clinical parameters.

### 9.2.5 **Assessments in participants who prematurely stop the study**

As stated in sections 7.4 and 8.5, If withdrawal is due to an AE, appropriate follow-up visits or medical care will be arranged, with the agreement of the subject's parent, until the AE has resolved, stabilised or a non-trial related causality has been assigned.

## 9.3 **Procedures at each visit**

Subjects will be asked to attend 4 visits at the Platform for clinical research in paediatrics over an 18-months study period (from 6 months to 24 months of age). The screening and pre-enrolment process will vary between participants and is not considered as a study visit. Each study visit is described in detail below. An overview is found in section 9.1.

### 9.3.1 **Screening: 0 to 6 months of age (between t-6m and t0)**

**Information about the trial:** The parents of potential subjects are informed about the trial via pamphlets, email, notice board and/or website/social media. The pamphlets include a pitch about the study and a QR code with a link to a website where they can read further information and access the participant informed consent form (PICF), with contact details for further questions. Interested parents are given the opportunity to talk with a member of the research team if they have any questions, and to consult the treating paediatrician prior to enrolment.

**Screening by investigators:** Parents of potential subject are then screened by investigators (or designee) that explains to the parent of each subject the nature of the study, its purpose, the procedures involved, the expected duration, the potential risks and benefits and any discomfort it may entail. The parent of each subject is informed that the participation in the study is voluntary, that they may withdraw their children from the study at any time, and that withdrawal of consent will not affect subsequent medical assistance and treatment. The parents of each subject are informed that they can ask any question, and consult with family members, friends, treating physicians or other experts before deciding about their participation in the study. Enough time is given to the parents of the subjects.

### 9.3.2 Visit 1: Baseline and randomisation, 6 months of age ( $t_0 \pm 2$ weeks)

**Eligibility check** by investigators, with review of past medical history and of vaccination records, re-evaluation of inclusion and exclusion criteria.

**Target clinical examination** will be performed if needed, to ensure that there is no temporary exclusion criteria (e.g. if the child is sick, the inclusion can be delayed a few days until the illness resolves).

**Overview of the trial** by investigators, using the study flow chart and the participant informed consent form. Correct comprehension of the trial will be checked, with the possibility for parents to ask any remaining question.

**Blood collection will be discussed** in further details for interested parents.

**Further information** will be given to all parents, including that

- The treating physician of their child will be contacted to inform about the trial, corroborate their child's medical history and seek additional information.
- Authorised individuals other than their treating physician may examine their child's medical records.
- The blood samples taken as part of the study will be coded and stored for a period of maximum 15 years; this duration has been chosen given the likelihood that progress in the nascent field of non-specific effects of vaccines may benefit substantially from the reanalysis of study samples. Upon the approval of the Sponsor, samples may be sent outside of Switzerland to collaborating research laboratories for non-commercial research purposes.
- There is no compensation for participating in the trial.
- They are free to withdraw at any time. Unless they specifically request complete consent withdrawal, the long-term data collection, including access to medical records, will continue, in order to avoid bias as much as possible.

**Informed consent** will be sought, once the subject's parent confirm understanding and voluntarily agreeing in participating; the parent and the investigator will both date and sign the consent form.

**Inclusion in the trial**, the parent is given a copy of the signed document; the original copy is securely filed in the study documentation.

**Baseline questionnaire** will be filled down by the subject parents and reviewed with the investigator. It includes questions on demographics, medical history, and exposure, as detailed in Table 4 in section 9.2.

**Eczema assessment** will be performed, using *SCORAD* score.

**Part 2 only: blood will be collected** (maximum 15 ml), in subjects whose parent accepted blood collection, for the laboratory tests listed in section 9.2.2. This is done after informed consent is obtained but prior to randomisation. In the eventuality that the blood collection fails, the subject will be considered as not consenting to blood tests (participation to Part 1 only), given that the laboratory analysis in Part 2 cannot be made in the absence of a baseline blood sample.

**Randomisation** in the trial, using a web-based randomisation procedure integrated into REDCap, stratified by consent to blood tests (yes/no), in randomly permuted blocks of variable length (4 or 8), enabling to prevent predictability of intervention assignments.

**Distribution of the vaccination plan** according to the group the subject has been randomised to.

**Group M.C. or M.M. only: MMR vaccination (first dose)**; Subjects randomised to the Group M.C. or M.M. (modified schedule for the 1st MMR dose) will receive one dose of MMR vaccine. After reconstitution of the vaccine by adding the entire content of the pre-filled syringe of solvent to the vial containing the powder, the vaccine (0.5 ml) will be injected intramuscularly in the deltoid region or in the anterolateral area of the thigh. The subject will be distracted during the injection, in order to minimise the pain. The subject will remain under close observation for 20 minutes after the injection.

**Group C.M. or C.C. only: No vaccination**; Subject randomised to the Group C.M. or C.C. (current schedule for the 1st MMR dose) will not receive any vaccine at 6 months.

**Vaccine diary** will be presented to the parents, who will be instructed to fill it for the next 42 days.

**Fortnightly questionnaire** will be presented to the parents, who will be instructed to fill them every 2 weeks for the next 18 months.

**Contact details** will be given to the parent, consisting in an emergency card with a phone number to call in case of questions about the trial or upon occurrence of any adverse event.

**Scheduling** next visits.

Once the subject and their parent have left:

**Data entry** will be checked by the investigator to ensure that no information is missing. Parents could be contacted if any data is missing.

**Contact with treating paediatrician** will be made, to inform about the inclusion and the randomisation, confirm the understanding of the trial procedures and the vaccination plan, and answer any questions.

### 9.3.3 Visit 2: Follow-up, 9 months of age ( $t_{+3m} \pm 2$ weeks)

**Review of the fortnightly questionnaires** by investigators, together with the parent, to ensure concordance and the absence of missing data; instruction to continue to fill them every 2 weeks until the subject is 24 months old.

**Review of vaccine diary**, by investigators, together with the parent, to ensure concordance and the absence of missing data; instruction to fill a second vaccine diary the next 42 days.

**Review of vaccination records**, by investigators, to ensure that all is in order. Review with the parent the vaccination plan and ensure it is well understood.

**Overview of the next steps of the trial** by investigators, using the study flow chart to ensure correct comprehension of the parent, with the possibility for parents to ask any question.

**Target clinical examination** will be performed if needed, to ensure that there is no temporary contra-indication for the vaccination (e.g. if the child is sick, the vaccination can be delayed a few days until the illness resolves) or for the blood test (e.g. if the child is sick or recovering, the visit can be delayed a few days until the illness resolves, as it might influence the laboratory test).

**Eczema assessment** will be performed, using SCORAD score.

**Part 2 only: blood will be collected** (maximum 15 ml), in subjects whose parent accept blood collection, for the laboratory tests listed in section 9.2.2. In the eventuality that the blood collection fails or if parents does not accept blood collection at this visit, the subject will remain in Part 2, as they have already provided a baseline blood and further blood collection might succeed.

**Group C.M. or C.C. only: MMR vaccination (first dose)**; Subject randomised to the Group C.M. or C.C. (current schedule for the 1st MMR dose) will receive one dose of MMR vaccine. After reconstitution of the vaccine by adding the entire content of the pre-filled syringe of solvent to the vial containing the powder, the vaccine (0.5 ml) will be injected intramuscularly in the deltoid region or in the anterolateral area of the thigh. The subject will be distracted during the injection, in order to minimise the pain. The subject will remain under close observation for 20 minutes after the injection.

**Group M.C. or M.M. only: No vaccination**; Subject randomised to the Group M.C. or M.M. (modified schedule for the 1st MMR dose) will not receive any vaccine at 9 months.

**Scheduling** next visits.

Once the subject and their parent have left:

**Data entry** will be checked by the investigator to ensure that no information is missing. Parents could be contacted if any data is missing.

**Contact with treating paediatrician** will be made, to ensure concordance of the data collected with the medical record and the absence of missing data, as well as to confirm the understanding of the next step of the trial and answer any questions.

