## 6. STUDY DESIGN

### 6.1 General study design and justification of design

#### 6.1.1 Study design and framework

This is a phase IV, single-center, open-label, randomised controlled trial with a factorial design, aiming to demonstrate the superiority of a modified vaccination schedule, compared with the current Swiss vaccination schedule for MMR.

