#### 6.2.2 Blinding procedures

Investigators involved in data cleaning and analyses will be blinded to allocation in order to avoid the introduction of bias between study arms, until statistical analyses have been completed.

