### 6.4 Risk mitigation of the trial design

**Variability in infectious risk:** Individual risk of infection depends on host (predisposition) and environmental (exposure) factors. Randomisation should ensure that risk factors are equally distributed between the two groups. The risk of those factors influencing the outcomes is also addressed by adjusting the analyses by the presence of comorbidities (host predisposition), siblings and day-care attendance (environmental exposure).

**Recruitment:** Recruitment will be through a network of private paediatricians highly motivated in contributing to clinical research. Pamphlets will be distributed in maternity services and paediatricians' offices; infants will be recruited during the first few months of age and parents will have opportunity to ask questions before the randomisation visit at 6 months of age. With over 5000 live births per year in Geneva, a minimum acceptance rate of 5% for Part 1 (questionnaires only) and of 1% for blood testing will enable recruitment to be completed in 18 months.

**Study burden / acceptance of the study:** The online questionnaire is being designed in partnership with parents in order to make it as user-friendly as possible. It will be completed every 2 weeks by participants' parents on a smartphone, computer or tablet following a participant-specific link sent by text or email, and will take less than 10 minutes to complete. The questionnaire includes many fields per participant but, thanks to branching algorithms, only items relevant to each participant will be displayed (based on the answers to previous questions). This design reduces redundancy and reduces the risk of missing or duplicate data.

**Accuracy of parent-reported data:** The questionnaire uses pre-filled fields, drop-down menus, and other measures to reduce the time taken for completion, and to increase the accuracy of the data. The data will be reviewed with the treating paediatrician, and the parents during the clinic visit, to retrieve any missing information. The child's medical records will also be checked. Clinical assessment will take place during the study visit to confirm some of the outcomes (e.g. presence of eczema using validated scores).

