Allergic disease outcome data: presence of eczema, food allergy, wheezing disease.  Eczema - diagnosis using adapted version of the UK diagnostic tool,  parent-reported doctor-diagnosed, and clinical evaluation during study visits; symptoms; severity and impact on quality of life using the POEM  and the SCORAD  scores.  Food-allergy – parent-reported doctor-diagnosed food allergy or sensitisation; diagnostic test used: participants with suspicion of food allergy will be seen by a specialist, as routinely done in Geneva. As recommended,  diagnosis will be made using oral food challenge, basophil activation test, or mast cell activation test; sensitisation defined using skin prick tests results and serum-specific IgE concentration (including allergen component-resolved diagnostics).  Wheezing diseases – parent-reported doctor-diagnosed wheezing episode (bronchiolitis or infant asthma).   For each allergic disease: age at diagnosis, date, duration and severity of episodes/flare, outcome, treatment.
Potential confounding factors post randomisation: breastfeeding (age at cessation); formula (type); solid feeding (age at introduction of different foods); smoking exposure; childcare attendance (index & siblings); travel; pet exposure; vitamin D supplementation; probiotic intake; paracetamol/ibuprofen use; antibiotics; other vaccinations (which and when).

Table 4: Summary of clinical data that will be collected.

\* Collection of participants' date of birth is needed to determine the season of birth (see table 4 above), as well as the time range for the visits (see section 9.3).

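### No masked SCORAD assessor is named, and the visit order puts vaccine diary and vaccination record review before scoring; separately, the paired tests named for continuous outcomes do not compare the randomised groups

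*Protocol*

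**What the plan says.** Section 6.4 of the protocol, under the accuracy of parent-reported data, says: "Clinical assessment will take place during the study visit to confirm some of the outcomes (e.g. presence of eczema using validated scores". Eczema is the only example given. Table 4 in section 9.2 bases the eczema diagnosis on an adapted UK diagnostic tool, "parent-reported doctor-diagnosed, and clinical evaluation during study visits", and measures severity by POEM and SCORAD. Section 9.2.2 lists SCORAD among the severity measures for AIMS 2 and 4.

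On masking, section 6.1.1 says: "This is a phase IV, single-center, open-label, randomised controlled trial with a factorial design". Section 3.6 rules out a placebo injection. Section 6.2.2 says only: "Investigators involved in data cleaning and analyses will be blinded to allocation in order to avoid the introduction of bias between study arms".

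On visit order, section 9.3.3 (Visit 2) has investigators review the questionnaires, then the vaccine diary (with "instruction to fill a second vaccine diary the next 42 days"), then the vaccination record, "by investigators, to ensure that all is in order. Review with the parent the vaccination plan and ensure it is well understood". The next steps of the trial and a targeted examination follow. Only then is the eczema assessment listed, which "will be performed, using SCORAD". Section 9.3.4 (Visit 3) keeps this order. Section 9.3.5 (Visit 4) lists questionnaires, diary and vaccination record before SCORAD. Section 9.3.2 (Visit 1) lists SCORAD before randomisation.

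On analysis, section 11.4.3 names the paired t-test or the Wilcoxon signed-rank test for continuous outcomes at 9 months and 2 years. Section 11.4 leaves full details to the statistical analysis plan.

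**The concern.** An examination confirms a parent's report only if it does not share the parent's knowledge. Parents know which schedule their child follows. If the person scoring SCORAD has also just read it from the child's vaccination record, both sources can lean the same way, and their agreement is weaker evidence than section 6.4 implies. The lean would tend to favour the trial's own hypothesis in section 4.3 that the modified schedule reduces atopic disease.

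At 9 months the record shows whether MMR was given at 6 months, which is the Stage A allocation. At 24 months it shows the timing of both doses. Visit order and assessor masking are matters of conduct, fixed in section 9.3. No later analysis can undo a score given with knowledge of allocation.

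The second matter is smaller. A baseline SCORAD is collected before randomisation, yet the tests named for continuous outcomes are within-child tests. They show how a child's score changes, not whether the randomised groups differ.

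**Working it through.** **The plan's own figure.** The only clinical sample size is for the primary outcome. Section 11.2 gives a control rate of 0.29 episodes per month, SD 0.32, a 30% reduction, 80% power, two-sided 0.05 and 85% completion.

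- Difference: 0.29 × 0.30 = 0.087.
- n per group = 2 × (1.960 + 0.842)² × 0.32² / 0.087² = 212.4, rounded up to 213.
- Allowing for 15% loss: 213 / 0.85 = 250.6, so 251 per group and 502 in total, against 500 stated. This reproduces and is not in dispute.
- Evaluable per group: 0.85 × 250 = 212.5. The 85% refers to the 9-month questionnaire. Using it for SCORAD attendance is my assumption.

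**Visit order, from sections 9.3.2 to 9.3.5.**

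| Visit | Listed before SCORAD |
|---|---|
| 1 (6 months) | No allocation yet; randomisation comes later |
| 2 (9 months) | Diary, vaccination record, vaccination plan |
| 3 (12 or 13 months) | Diary, vaccination record, vaccination plan |
| 4 (24 months) | Diary, vaccination record |

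So every score after randomisation is exposed. At Visits 2 and 3 SCORAD is already listed before that visit's injection, so moving it earlier does not disturb vaccination.

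**What a scoring shift would do.** The protocol gives no SCORAD SD and no eczema prevalence, so the shifts below are assumptions. There is no true effect in either illustration.

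*Continuous score.* SE = √(2/212.5) = 0.0970 SD. The false-positive rate under a systematic shift b is Φ(b/SE − 1.96) + Φ(−b/SE − 1.96).

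| Shift b (SD) | b/SE | Unadjusted | Adjusted for Visit 1, r = 0.5 |
|---|---|---|---|
| 0.05 | 0.52 | 8% | 9% |
| 0.1 | 1.03 | 18% | 22% |
| 0.2 | 2.06 | 54% | 66% |

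Adjustment makes the false-positive rate slightly higher, because it shrinks the SE and leaves the shift in place.

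*Presence or absence.* Assume that 20% truly have eczema in both groups, with 212 per group, and that 10%, 20% or 30% of cases in the early-MMR group are scored as clear. The comparison becomes 0.20 against 0.18, 0.16 or 0.14. With pooled SE √(2p̄(1 − p̄)/212):

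- 0.18: SE 0.0381, z = 0.525, rejection 8.2%.
- 0.16: SE 0.0373, z = 1.072, rejection 18.8%.
- 0.14: SE 0.0365, z = 1.645, rejection 37.6%.

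**What the Visit 1 score would add.** Under analysis of covariance the residual variance is multiplied by 1 − r², where r is the correlation between the Visit 1 score and the later score (assumed). The difference detectable with 80% power is (1.960 + 0.842) × 0.0970 × √(1 − r²).

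| r | Variance removed | Detectable difference (SD) | Power at 0.272 SD |
|---|---|---|---|
| Unadjusted | 0% | 0.272 | 80% |
| 0.3 | 9% | 0.259 | 84% |
| 0.5 | 25% | 0.235 | 90% |
| 0.7 | 49% | 0.194 | 98% |

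**The case against.** Several objections have force.

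- *The assessor is not identified.* The eczema step is written in the passive, and nothing says the person who reads the record also scores. That the scorer is unmasked is an inference. It is a strong one, because the trial is open-label, section 6.2.2 stops at cleaning and analysis, and no separate assessor appears anywhere.
- *SCORAD is not the only eczema measure.* Table 4 lists several others, and the paediatrician and medical records are also consulted. This stands, although none of those sources is described as masked, and the paediatrician is told of the randomisation (section 9.3.2).
- *Section 6.4 speaks of accuracy, not of open-label bias.* A reader might infer that SCORAD was offered as a remedy for unblinded parent reporting. The protocol does not say that. It gives the examination a confirming role, and that is enough for the point.
- *The Visit 1 score is not excluded.* A reader might infer that SCORAD will be compared without it. The documents do not support this. The score is collected, the named tests are paired and could use it within a child, and the covariate list is a normal matter for the statistical analysis plan. What can be faulted is that paired tests are named where randomised groups are to be compared.
- *Masking will be incomplete.* Parents may talk, and staff at a single centre may remember. Visit 3 timing (12 or 13 months) reveals the second-dose arm, and that visit may be delegated to the treating paediatrician. All true, but scoring before opening the record is still better than scoring after it.

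**Conclusion.** The point holds in a limited form. The protocol uses the visit examination to confirm parent-reported eczema, provides no masking of the SCORAD assessor, and lists allocation-revealing reviews before SCORAD at Visits 2, 3 and 4. The vaccination plan is part of those reviews at Visits 2 and 3 only.

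The size of any bias cannot be derived from the protocol. Under the assumed shifts, a nominal 5% error becomes anything from 8% to 54% on the continuous scale, or 8% to 38% for presence of eczema. These figures show sensitivity; they do not predict what will happen.

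Separately, the tests named in section 11.4.3 do not compare the randomised groups for a continuous outcome such as SCORAD. Using the Visit 1 score as covariate is a gain in precision whose size depends on an assumed correlation. It is no remedy for assessor bias.

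The point concerns one of several eczema measures for a secondary outcome. The primary outcome, respiratory infections from 6 to 9 months, is unaffected. The change is worth making mainly because it costs so little.

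**What to change.** 1. In sections 9.3.3 and 9.3.5, make SCORAD the first procedure of the visit, entered and locked in REDCap before the diary, vaccination record or vaccination plan is opened. Do the same in section 9.3.4 as far as its timing and possible delegation allow.
2. Ask parents beforehand not to mention vaccines until the skin has been scored.
3. Where existing staffing allows, have SCORAD done by someone who did not vaccinate that child. Extend section 6.2.2 to say what masking of the assessor is attempted and where it is expected to fail.
4. In section 11.4.3, replace the paired tests for continuous outcomes with a between-group comparison. For SCORAD at Visits 2 and 4, use a model with randomised group and the Visit 1 SCORAD as covariate, detailed in the statistical analysis plan.

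Cost: a reordering of existing visit steps, a lock on one form, and some wording. No new visit or measurement is needed. The remaining weakness is that masking stays partial, and the report should say so when it sets SCORAD beside parent-reported eczema.
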